The sample size for this investigation is determined for the primary endpoint of total propofol dose in the first 4 hours. Basuni (2014) reported differences in propofol dose of approximately 0.7 SD for patients receiving saline vs lidocaine+bicarb.

The current investigation is considered a randomized Phase II study, with the objective of determining whether or not additional studies of the current treatment intervention are warranted. Although debate exists regarding the value of formal statistical comparisons in phase II trials, we agree with those who propose that a one-sided test with a false-positive (type I error) rate of 0.10 for the primary endpoint is an appropriate criterion to use to help guide the decision-making process. In general, a sample-size of N=20 patients per group will provide statistical power (one-tailed, alpha=0.10) of 80% to detect a difference between groups of 0.7 standard deviation units.

Data Collection:

Regarding the primary outcome, total sedation required from the time of the patient entering the ICU until extubation, will be recorded in the electronic charting documentation.

Regarding a secondary outcome, the total amount of time the patient is intubated (from the time they enter their room in the ICU from surgery) will be recorded by the RRT on the assessment form provided.

Regarding the secondary outcomes, patient assessment forms will be provided in the envelopes (attached to patients chart) for the study team, SRNA, to fill out. Completed assessments will be collected at the end of each day and will be manually analyzed at the end of the study once the sample size is reached.

Data Analysis

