Data will be summarized using mean \pm SD, or median [25th, 75th] for continuous variables and frequency counts and percentages for nominal variables. The primary endpoint will be sedative dose (Propofol, precede, fentanyl, ketamine) amount from the mechanical ventilation weaning protocol initiation until ETT extubation. This endpoint will be compared across groups using the two-sample t-test, or rank sum test. Secondary endpoints will include; time to extubation (from initiation of the mechanical ventilation weaning protocol); and coughing, restlessness, hoarseness, and dysphagia. Sedative dose will be treated as continuous variables and analyzed using ANOVA. Post-extubation endpoints will be dichotomized and analyzed using logistic regression. In all cases, distributional assumptions will be assessed with transformations or nonparametric methods used as appropriate.

Statistical Analysis:

Recorded characteristics will be presented using mean \pm SD or median (IQR) for continuous variables and frequency percentages for categorical variables. Summaries of these variables will be presented overall. The primary outcome will be compared using analysis of variance (ANOVA). Secondary analyses will also be performed and analyzed using logistic regression. Two-tailed p-values ≤ 0.05 will be considered statistically significant in all analyses.

Strengths

Despite variation in co-morbidities and surgery types, all patients deemed rapid recovery eligible have necessarily undergone screening for complications, hemodynamic stability, adequacy of hemostasis, and anticipated readiness for extubation within 2 to 6 hours. This improves the generalizability of study results. All patients have the added benefit of being closely and safely monitored by the cardiac ICU team during the entire duration of the intervention. There will be a pharmacist on the ICU as well to help with any discrepancies that may arise. The study is using a sample size with sufficient enough power to gain a greater separation of results between the control and intervention arms.

Limitations

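### The trial is sized on a one-sided 0.10 test of the primary endpoint, but the analysis section sets two-tailed 0.05 for every analysis; power at 0.7 SD is about 82% under the first rule and about 58% under the second

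*Combined protocol and SAP*

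**What the plan says.** The Sample Size section describes the study as a randomized Phase II trial meant to show whether further studies are warranted. It argues that "a one-sided test with a false-positive (type I error) rate of 0.10 for the primary endpoint is an appropriate criterion" to help guide that decision. It then states that 20 patients per group give "statistical power (one-tailed, alpha=0.10) of 80% to detect a difference between groups of 0.7 standard deviation units".

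Two sections further on, Data Analysis names the test for the primary endpoint: "This endpoint will be compared across groups using the two-sample t-test, or rank sum test". Statistical Analysis names ANOVA for the same outcome and closes with the significance rule: "Two-tailed p-values ≤ 0.05 will be considered statistically significant in all analyses". That sentence stands in the same paragraph as the primary-outcome ANOVA and does not set the primary endpoint apart.

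The Strengths section then asserts: "The study is using a sample size with sufficient enough power". It does not say under which significance rule.

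**The concern.** A power statement holds only for the test it was calculated for. Here the primary endpoint has two success criteria that differ in both sidedness and alpha, and both are current text. Read literally, the rule in Statistical Analysis covers the primary endpoint, and the trial then has much less power than Sample Size promises.

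This bears on the purpose of the study. Its primary test is meant to inform whether intracuff lidocaine deserves further study. With two thresholds on the page, a result between them supports either conclusion, and the choice could be made after the p-value is known. If the stricter rule is used, the chance of missing the planned effect rises from about 18% to about 42%.

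**Working it through.** **Inputs, all from the combined protocol and SAP**

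- Sample Size: n = 20 per group; difference 0.7 SD (so SD = 1); one-sided alpha 0.10; stated power 80%.
- Statistical Analysis: two-sided alpha 0.05, in all analyses.
- Data Analysis and Statistical Analysis: two-sample t-test or rank sum test; ANOVA.
- No dropout allowance is stated, so none is applied.

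**Method.** Two-sample t-test, power from the noncentral t distribution.

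- Degrees of freedom: 2 × 20 − 2 = 38.
- Noncentrality: 0.7 × √(20/2) = 0.7 × 3.162 = 2.214.

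**Step 1: reproduce the plan's figure (one-sided 0.10).** The critical value is t(0.90; 38) = 1.304. Power = P(T > 1.304 | ncp 2.214) = **81.8%**. The normal approximation gives Φ(2.214 − 1.282) = 82.4%. The smallest n giving 80% is 19 per group by either method. The stated 80% with 20 per group is therefore sound for its own inputs.

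**Step 2: apply the rule in Statistical Analysis (two-sided 0.05).** The critical value is t(0.975; 38) = 2.024. Power = P(|T| > 2.024 | ncp 2.214) = **57.8%**. The normal approximation gives Φ(2.214 − 1.960) = 60.0%.

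**Step 3: what 80% power would need at two-sided 0.05.** At 0.7 SD, 33 per group gives 79.97% and 34 per group gives 81.2%, so 34 per group. With 20 per group, the effect detectable with 80% power is 0.91 SD.

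**Step 4: the observed difference that counts as significant.** This is the critical t × √(2/20) = critical t × 0.3162.

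- One-sided 0.10: 1.304 × 0.3162 = 0.41 SD.
- Two-sided 0.05: 2.024 × 0.3162 = 0.64 SD.

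**Step 5: how often the two rules disagree.** With a true effect of 0.7 SD: 81.8% − 57.8% = **24.0%** of trials would be significant under the first rule only. With no effect, counting results that favour lidocaine: 10% − 2.5% = 7.5%.

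**Step 6: does the choice of test change this?** Simulation of the rank-sum test with normal data gives about 80% and 56% under the two rules. A large-sample approximation (relative efficiency 0.955) gives about 81% and 58%. The gap comes from alpha and sidedness, not from the test.

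| Rule | Power at 0.7 SD, t-test | Observed difference needed |
|---|---|---|
| One-sided 0.10 (Sample Size) | 81.8% | 0.41 SD |
| Two-sided 0.05 (Statistical Analysis) | 57.8% | 0.64 SD |

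**The case against.** The best defence is that the specific text should prevail over the general. Sample Size names the primary endpoint, gives a reason for the one-sided 0.10 test and builds the design on it. The sentence in Statistical Analysis is a general closing line. On that reading power is about 82% and nothing is lost. This may well be what was intended, and for that reason 58% cannot be given as the trial's power without a condition. It does not remove the conflict, because the general sentence expressly covers all analyses and no text ranks one rule above the other.

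A second defence is that this is a small feasibility study and that the criterion only helps to guide a decision. That stands in part: a result between the thresholds would not automatically end or continue development. Still, the plan chose a formal test with a stated alpha and power, and a guide with two thresholds guides poorly.

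A reader might also infer three stronger things that the documents do not support.

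- **That the 80% is an arithmetic error.** It is not; step 1 reproduces it.
- **That naming ANOVA rules out a one-sided test.** It does not. With two groups F = t², so an F-test p ≤ 0.20 with the lidocaine mean lower is the one-sided 0.10 test. The F(1,38) critical value at 0.20 is 1.701, the square of 1.304. Only the 0.05 threshold conflicts.
- **That naming a t-test in one place and ANOVA in another is a conflict of method.** For two groups, ANOVA and the equal-variance t-test give the same two-sided p-value. The rank sum option is covered by the plan's provision for nonparametric methods where distributional assumptions call for them. Whether to fix one test in advance is a separate, optional matter.

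**Conclusion.** The concern holds as an internal inconsistency: the primary endpoint has two incompatible significance criteria. At 20 per group and 0.7 SD, power is about 58% if the rule in Statistical Analysis governs and about 82% if the rule in Sample Size governs. About 24% of trials under the planned effect would be significant under one rule and not under the other. The sufficiency claim under Strengths is supported only under the one-sided 0.10 rule.

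The figures assume normal data with equal variances, 20 analysed patients per group, and a 0.7 SD effect that carries over to the endpoint analysed. The last assumption is open. Sample Size takes 0.7 SD from propofol dose against a saline cuff, whereas this trial compares with air, and Data Analysis specifies a dose of several sedatives from the start of weaning to extubation. At two-sided 0.05 with 20 per group, power would be about 34% at 0.5 SD and 79% at 0.9 SD. This uncertainty affects the power figures but not the conflict between the two rules.

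**What to change.** Choose one rule and state it in both sections before the data are analysed.

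**Option A, keeping the design as sized.** In Statistical Analysis, state that the primary endpoint is tested one-sided at alpha 0.10, in the direction of a lower sedative dose with lidocaine than with air, and that two-tailed p ≤ 0.05 applies to the other analyses only. Where the t-test or ANOVA is used for the primary endpoint, report the one-sided p-value.

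**Option B, keeping two-tailed 0.05 for the primary endpoint.** In Sample Size, drop the one-sided 0.10 criterion and restate the power as about 58% at 0.7 SD, with 80% reached only at about 0.91 SD. Remove the sufficient-power statement from Strengths.

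Both options change wording only and need no extra patients. Keeping both two-tailed 0.05 and 80% power at 0.7 SD would need 34 per group, which is 68 − 40 = 28 more patients. Naming a single test in advance, t-test or rank-sum, would be a reasonable addition, but the conflict can be resolved without it.

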- Cardiac surgery includes: single valve repair, myectomy, CABG, pericardectomy.
- Patients who are anticipated to be deemed, "rapid recovery," in the cardiac surgery ICU at St. Mary's Hospital
-

Exclusion Criteria:

- Age < 18 years old at time of surgery
- Patients who cannot consent themselves or non-English speaking patients who require an interpreter
- Patients who are not sent to the cardiac ICU post-operatively
- Patients who are anticipated to have a difficult tracheal intubation
- Patients having risk factors of postoperative aspiration of gastric contents
- Patients who have respiratory disease or recent respiratory tract infection
- > 2 attempts to secure an airway
- Patients undergoing TAVR procedures or any form of "robotic," procedures

Methods:

Patients will be chosen based on their inclusion/exclusion criteria. Patients during their clinic appointment prior to surgery were provided a thorough explanation of the intervention and study, if the patient agrees to participate; he or she will be included in the study. The day of the procedure, the patient will have the intervention take place while in the operating room by the Registered Respiratory

Therapist (RRT), Certified Registered Nurse Anesthetist (CRNA) or Anesthesiologist. The patient will remain intubated after the surgery is complete and will be taken to the cardiac surgical ICU.

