At the induction of anesthesia, patients will be breathing 100% oxygen via a face mask and then, become anesthetized according to a standard protocol and at the discretion of the attending anesthesiologist. Patients will be receiving fentanyl, lidocaine (as an IV anesthetic preventing uncomfortable side effect Propofol can create in the arm) and either succinylcholine or vecuronium to facilitate tracheal intubation. Laryngoscopy will then be performed and the trachea intubated with a standard cuffed ETT. ETT tubes from 6.0mm to 8.0mm in diameter will be used. Inflation of the ETT cuff will be performed in accordance with the randomization of either air or 1.8% lidocaine/0.76% solution until such time as there is no air leak around the tube when administering positive pressure to 20 cm H₂O. Checking for intermittent leaks to ensure a minimum seal is present will be done as needed per standard of care. Anesthesia will be maintained with volatile anesthetic with or without a Propofol infusion. Vecuronium will be used to maintain the ulnar nerve train-of-four at 0–3 of four twitches. Anesthesia maintenance will occur until the near end of the surgical procedure. The volatile anesthetic will be discontinued and Propofol will be initiated via a continuous infusion to facilitate transportation to the intensive care unit (ICU). After arrival to the ICU, Neuromuscular blockade will then be antagonized with suggamadex reversal agent, and the pharynx being gently suctioned under direct vision. Mechanical ventilation to be maintained until swallowing or spontaneous respiration begins, and then, converted to assisted manual ventilation. Extubation will be performed at ICU provider's discretion once the extubation protocol criteria are met.

The patient then will be closely monitored as a 1:1 by the room nurse, and by other staff (respiratory therapist, and ICU fellows and consultants) for toleration of the ventilator (coughing, double triggering, "bucking," etc.) on the cardiac surgical intensive care unit. Sedation amount will be recorded electronically from initiation of the mechanical ventilation weaning protocol until the time of extubation. The RRT will physically record "yes," or "no," on the form provided regarding the patient coughing, complaining of a sore throat or difficulty swallowing, having hoarseness or difficulty speaking.

Sample Size:

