In addition, the potential risks that have been investigated in the literature for this topic are comprised of: two meta-analyses, many randomized-controlled trials, and one retrospective case-control study. The majority of this evidence is level II, with two level I meta-analysis on the Ackley level of evidence scoring tool, indicating a high level of quality, reliability, and generalizability, with a low risk of bias among the evidence.¹ For over 20 years, researchers have been experimenting with lidocaine to help patients overcome the various side effects and complications of being intubated. There have been a few studies conducted to determine the safety and efficacy of lidocaine diffusion across the polyurethane cuff of the endotracheal tube.^{2,3} Both Estebe et al.⁴ and Huang et al.³ determined that alkalinization of lidocaine is safe to use, without compromising the integrity of the cuff and improves the diffusion when compared to lidocaine alone. Since these studies, most researchers have utilized alkalinized lidocaine in intracuff studies, and there have even been a few studies that have compared different concentrations of lidocaine.^{4,5} This high level of evidence will guide a protocol for the

anesthesia and intensive care staff at Mayo Clinic caring for rapid recovery cardiac surgery patients. This study will improve and elaborate on the science behind intracuff lidocaine and the positive impact on lowering patient sedation requirements, as well as, bridge the gap between current studies with endotracheal lidocaine and decreased sedation in the intensive care setting. While reviewing the literature, there were no reported cases of sentinel events or tube rupture.

With the scientific evidence, our team has also consulted with multidisciplinary groups across the campus to ensure safety and efficacy of this study. The critical care respiratory therapists group has been educated on the science behind this study, and their role in protecting the patient's airway. The respiratory therapists will continue to do all of their normal safety assessments, in addition to monitoring how much lidocaine is in the cuff upon arrival to the ICU and at extubation to ensure there is not over or under inflation. The team has also obtained approval from the Critical Care Service consultant group. This group of highly experienced physicians was briefed on the exact procedures that will take place throughout this study, including the benefits and potential risks.

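### Methods gives the yes/no symptom scoring to the respiratory therapist, a role that learns the arm from the cuff check; Data Collection names a different rater, and blinding is stated for neither

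*Combined protocol and SAP*

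**What the plan says.** Methods describes cuff inflation "in accordance with the randomization of either air or 1.8% lidocaine/0.76% solution", so one arm has gas in the cuff and the other liquid. Methods also lists the RRT among the staff who may carry out the intervention in the operating room.

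Potential Risks adds a duty for the respiratory therapists in the ICU: "monitoring how much lidocaine is in the cuff upon arrival to the ICU and at extubation".

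Two sections say who records the symptoms, and they differ:

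- Methods has the RRT enter yes or no "on the form provided regarding the patient coughing, complaining of a sore throat or difficulty swallowing, having hoarseness or difficulty speaking".
- Data Collection says of the secondary outcomes that "patient assessment forms will be provided in the envelopes (attached to patients chart) for the study team, SRNA, to fill out".

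Data Collection also has the RRT write down the intubation time, which "will be recorded by the RRT on the assessment form provided". Sedation amounts, by contrast, go into the electronic chart (Methods, Data Collection).

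Data Analysis dichotomizes the post-extubation endpoints and analyses them by logistic regression. Statistical Analysis sets two-tailed 0.05 for all analyses. The text available for review, which lacks the opening of the document, does not describe blinding of patient, assessor or ICU staff. Limitations does not raise the matter.

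**The concern.** Whether a patient coughed or sounded hoarse is a judgement, and a rater who knows the treatment can shift it without meaning to. Anyone checking how much lidocaine is in the cuff finds liquid in one arm and air in the other. The second check falls at extubation, close to when post-extubation symptoms would be scored. Potential Risks adds that the therapist group has been taught the rationale of the study, so these raters may hold an expectation as well as know the arm.

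At stake is most of Aim 3. With 20 patients per group, a few altered entries move a symptom rate noticeably, and the likely direction favours lidocaine. If the SRNA is the intended rater, the link through the cuff check does not apply directly, but the plan still does not say that this person is kept unaware of the allocation.

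**Working it through.** **1. The plan's own figure.** Sample Size claims 80% power with 20 per group, a difference of 0.7 SD and one-sided alpha 0.10. The noncentrality is 0.7 × √(20/2) = 2.21 and the critical t on 38 df is 1.304, which gives 81.8% power. The claim reproduces. The present point does not depend on it; only the 20 per group is carried forward.

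**2. The sections side by side.**

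| Task | Who | Where |
|---|---|---|
| May fill the cuff | RRT, CRNA or anesthesiologist | Methods |
| Checks lidocaine in the cuff at ICU arrival and extubation | Respiratory therapists | Potential Risks |
| Scores cough, sore throat, swallowing, hoarseness/speech | RRT | Methods |
| Fills in the secondary-outcome forms | Study team, SRNA | Data Collection |
| Records intubation time | RRT | Data Collection |

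Rows 2 and 3 put knowledge of the arm and subjective scoring in one role. Rows 3 and 4 cannot both describe the rater of the same symptoms.

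**3. Endpoints affected.** Aim 3 lists sore throat, cough, dysphonia, dysphagia, restlessness and agitation. The RRT's list in Methods covers the first four. Restlessness and agitation are not on it.

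**4. Size, by illustration.** The documents give neither symptom rates nor any measure of rating error, so both are assumed. Let the true symptom rate be p in both arms (no treatment effect). Let a fraction m of true symptoms go unrecorded in the lidocaine arm only, so that the recorded rate there is p(1 − m). With x₁ and x₂ recorded symptoms among 20 per arm and p̄ = (x₁ + x₂)/40, the test rejects when

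|x₁ − x₂|/20 ÷ √(2p̄(1 − p̄)/20) ≥ 1.96.

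This is the pooled two-proportion test, equivalent to the score test in a logistic regression on arm alone. The false-positive rate is the sum of Bin(x₁; 20, p) × Bin(x₂; 20, p(1 − m)) over all rejecting pairs, by exact enumeration:

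| True rate p | m = 0 | m = 10% | m = 20% | m = 30% |
|---|---|---|---|---|
| 30% | 5.3% | 5.8% | 7.3% | 10.1% |
| 50% | 4.3% | 5.3% | 8.7% | 15.0% |
| 70% | 5.3% | 7.9% | 15.0% | 26.4% |

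For example, at p = 50% and m = 20% the recorded lidocaine rate is 0.50 × 0.80 = 40%: on average 8 of 20 recorded against 10 of 20, a spurious difference of 10 percentage points.

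**The case against.** The strongest reply is that Data Collection already names the SRNA, so the therapist may not be the rater at all. That is a fair limit on certainty: what the documents prove is a conflict, with an allocation-aware role on one side of it. It does not remove the point, because Methods names the RRT explicitly and neither section says the rater is blinded.

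Several stronger readings are tempting and are not supported:

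- A reader might infer that one individual therapist checks the cuff and scores the same patient. The documents link the tasks by role only. Equally, nothing separates them.
- A reader might infer that all of Aim 3 is affected. Restlessness and agitation are not on the RRT's list, and sore throat and difficulty swallowing are partly patient complaints.
- A reader might carry the bias over to the primary endpoint. For a continuous endpoint at one-sided 0.10 with 20 per arm, a bias of 0.1, 0.2 or 0.3 SD would raise false positives from 10% to 17%, 26% or 37%; at two-sided 0.05 the same biases give 6.1%, 9.5% and 15.2%. Those figures do not describe dichotomized symptoms, and the RRT does not score sedative dose. Unblinded titration would be a separate matter.
- A reader might take two misrecorded patients as enough for a false finding. They are not: 10/20 against 8/20 gives p = 0.53 (chi-square) or 0.75 (Fisher). The inflation comes from a systematic shift added to chance variation.
- A reader might treat the RRT's record of intubation time as equally exposed. It is a clock time, so who writes it down matters little; who decides on extubation matters more.

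It also stands that these are secondary endpoints in a small feasibility study whose formal decision criterion is the primary endpoint.

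**Conclusion.** The point holds in this form. Methods and Potential Risks together give subjective scoring of four symptom groups to a role that learns the allocation. Data Collection contradicts Methods on the rater, and no safeguard is stated in the text available.

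At 20% one-sided under-recording, the false-positive rate per symptom is about 7% to 15% rather than 4-5%; at 10% it is about 5% to 8%, and at 30% about 10% to 26%. These figures rest on assumed symptom rates and assumed under-recording, and on the two-arm randomized design in Methods and Sample Size, although the Description under Human Subjects speaks of a single group. They show what differential recording could do, not what will happen.

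This is a cheap improvement to the secondary outcomes. It does not show that the primary comparison is invalid.

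**What to change.** Reconcile Methods with Data Collection so that one rater is named throughout:

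- The SRNA already named in Data Collection completes the symptom form after extubation, using a fixed script. This person is not told the allocation and is not present at cuff filling, cuff checks or deflation.
- The RRT keeps the cuff check and does not score symptoms.
- The report states that sedation titration and extubation decisions were not blinded, if that is so.

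Sedation totals need no change, since they are already taken from the electronic chart. The documents do not say that extubation time is charted electronically, so the fix does not rely on it.

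The cost is wording in Methods and on the form, plus coordination. The SRNA must be able to see the patient at the assessment time, which the protocol does not give and should, and must stay away from the cuff check; otherwise the masking fails. Masking the SRNA also does not deal with what the patient knows, which matters for sore throat and difficulty swallowing.
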